2. LIST OF ABBREVIATIONS

See Medicine Glossary:
<http://glossary>

Term	Definition / description
ADA	Anti-drug antibody
ADS	Analysis data set
ALT	Alanine transaminase
AST	Aspartate transaminase
ATC	Anatomical Therapeutic Chemical
AU	Arbitrary units
AUC	Area under the curve
[REDACTED]	[REDACTED]
[REDACTED]	[REDACTED]
[REDACTED]	[REDACTED]
BCVA	Best corrected visual acuity
BLRM	Bayesian logistic regression model
BMI	Body mass index
BMS	Biomarker analysis set
CARE	Clinical data Analysis and Reporting Environment
CFB	Change from baseline
CI	Confidence interval
[REDACTED]	[REDACTED]
[REDACTED]	[REDACTED]
[REDACTED]	[REDACTED]
c-NRP-1	Neurolipin 1
CTP	Clinical trial protocol
CTR	Clinical trial report
CV	Arithmetic coefficient of variation
DBLM	Database lock meeting

Term	Definition / description
DLE	Dose limiting event
DRIL	Disorganisation of retinal inner layer
DRSS	Diabetic retinopathy severity scale
ECGPCS	ECG Pharmacokinetic Concentration Set
EDMS	Electronic documentation management system
EOS	End of Study
ES	Enrolled set
ETDRS	Early treatment diabetic retinopathy study
FAZ	Foveal avascular zone
gCV	Geometric coefficient of variation
gMean	Geometric mean
█	█
IOP	Intra-ocular pressure
IVT	Intravitreal
█	█
LLBCVA	Low luminance best corrected visual acuity
LOCF	Last observation carried forward
Max	Maximum
MD	Multiple dosing
MedDRA	Medical Dictionary for Regulatory Activities
MMRM	Mixed model for repeated measures
Min	Minimum
N	Number of non-missing observations
NEI	National Eye Institute
Nobs	Number of observations
OCTA	Optical coherent tomography angiography
P10	10 th percentile
P90	90 th percentile
█	█
PT	Preferred term
Q1	1 st quartile
Q3	3 rd quartile

Term	Definition / description
RAGe	Report Appendix Generator system
REP	Residual effect period
RPM	Report planning meeting
SCR	Screening
SD	Standard deviation
(SD-)OCT	(Spectral domain) optical coherence tomography
SOC	System organ class
SRD	Single rising dose
SUN	Standardization of Uveitis Nomenclature
█	█
█	█
TMF	Trial master file
TS	Treated set
TSAP	Trial statistical analysis plan
ULN	Upper limit of normal
VFD	Vessel flow density
█	█
WHO-DD	World Health Organization Drug Dictionary

3. INTRODUCTION

As per ICH E9 (1) the purpose of this document is to provide a more technical and detailed elaboration of the principal features of the analysis described in the protocol, and to include detailed procedures for executing the statistical analysis of the primary and secondary variables and other data.

This Trial statistical analysis plan (TSAP) assumes familiarity with the Clinical Trial Protocol (CTP), including Protocol Amendments. In particular, the TSAP is based on the planned analysis specification as written in CTP Section 7 “Statistical Methods and Determination of Sample Size”. Therefore, TSAP readers may consult the CTP for more background information on the study, e.g., on study objectives, study design and population, treatments, definition of measurements and variables, planning of sample size, randomisation.

Study data (including data entered in the RAVE EDC system and external data provided by suppliers) will be stored in a Clinical Data Repository (CDR).

The statistical analyses will be performed within the validated working environment CARE, including SASTM (current Version 9.4, by [REDACTED]), and a number of SASTM-based tools (e.g., macros for the analyses of AE data or laboratory data; Report Appendix Generator system (RAGe) for compilation/formatting of the CTR appendices).

4. CHANGES IN THE PLANNED ANALYSIS OF THE STUDY

All analyses as planned in the CTP will be performed and are described in more detail in this TSAP. The following changes as compared to the CTP will be done in the analysis:

[REDACTED]

An additional subject analysis set was defined: The enrolled set (ES) will be used for presentation of disposition.

The acceptable time windows for deviations from the scheduled time will be extended as compared to the clinical trial protocol (for further details, please see [Section 6.7](#)).

In the model-based analysis of secondary endpoints, a mixed model for repeated measures (MMRM) will be used instead of a generalized mixed linear model (see [Section 7.5.2](#)).

Sensitivity statistical analysis of the efficacy endpoints using last-observation-carried-forward (LOCF) will not be performed as the handling of missing data is taken into account within the MMRM approach.

[REDACTED]

[REDACTED]

5. ENDPOINTS

5.1 PRIMARY ENDPOINTS

Section 2.1.2 of the CTP:

Part A:

- *Number of subjects with ocular dose limiting events (DLEs) from drug administration until day 8 (7 days after treatment)*

Part B:

- *Number of subjects with drug related AEs from drug administration until EOS (end of study)*

Dose limiting events were defined in the CTP as the following ocular events:

Section 5.2.1 of the CTP:

A DLE is defined as the occurrence of any of the following events in the study eye within the evaluation period (7 days after drug administration):

- *Development of sterile endophthalmitis and/or sterile inflammation of the vitreous of grade 3+ according to the NEI (National Eye Institute) Grading of vitreous haze, and anterior chamber cells of 3+ according to the Standardization of Uveitis Nomenclature (SUN) working group grading scheme (see CTP Table 5.2.1: 1) and a duration of 5 or more days between day 1 and day 8*
- *Visual loss of more than 15 letters at any given time-point*
- *Persistent IOP over 30 mmHg for 3 days*
- *Signs of vascular occlusion in a 1st (the main branch) or 2nd degree (the vessel after the first bifurcation of the main branch) retinal vessel, including peripheral retinal hemorrhages in the area supplied by the occluded vessel (hemorrhage of the macula would not be included as this is a symptom of the disease)*

5.2 SECONDARY ENDPOINTS

5.2.1 Key secondary endpoints

This section is not applicable as no key secondary endpoints have been defined in the CTP.

5.2.2 Secondary endpoints

Section 2.1.3 of the CTP:

Part A:

- *Number of subjects with drug related AEs at EOS*
- *Number of subjects with any ocular AEs (eye disorders) at EOS*

Part B:

- *Change from baseline of the size of the FAZ (Foveal Avascular Zone) in optical coherence tomography angiography (OCTA) at visit 5*
- *Change from baseline of the size of the FAZ in optical coherence tomography angiography (OCTA) at visit 6*
- *Change from baseline of the size of the FAZ in optical coherence tomography angiography (OCTA) at visit 7*
- *Change from baseline of BCVA (Best Corrected Visual Acuity) at Visit 7*
- *Number of subjects with any ocular AEs (eye disorders) from drug administration until EOS*

5.4 OTHER VARIABLES

Section 5.2.2 of the CTP:

A complete physical examination will be performed at the time points specified in the CTP Flow Charts. It includes at a minimum general appearance, neck, lungs, cardiovascular system, abdomen, extremities.

Measurement of height and body weight will be performed at the time points specified in the CTP flowchart.

Age [years] will be determined as the difference between year of informed consent and year of birth.

BMI will be calculated as $\text{weight [kg]} / (0.01 * \text{height [cm]})^2$.

6. GENERAL ANALYSIS DEFINITIONS

6.1 TREATMENTS

For basic study information on treatments to be administered, assignment of treatment groups and selection of doses, please see CTP, Sections 3 and 4.

This phase I/IIa trial in patients with diabetic macular ischemia consists of 2 parts, a single-rising dose (SRD) part and a multiple dose (MD) part:

The single-rising dose part (Part A) of the trial with 3 dose groups is designed as non-randomized, open-label and uncontrolled. Each dose group consists of at least 3 evaluable patients, the highest dose groups consists of 6 patients.

The multiple dose part (Part B) is designed as double-masked, randomized and sham-controlled. Thirty patients will be recruited, in a 2:1 ratio of active treatment versus sham. Patients receive three administrations of trial medication [REDACTED].

For both parts, one eye will be selected, according to inclusion /exclusion criteria, as the study eye to be treated.

For details of dosage and formulation see [Table 6.1: 1](#):

Table 6.1: 1 Treatments and labels used in the analysis

Treatment	Short label
[REDACTED]	

Section 7.3.5 of the CTP:

For BI 765128, the residual effect period (REP) after IVT administration is not known. Therefore, all AEs with an onset between start of treatment and the respective EOS visit will be assigned to the on treatment period for evaluation. The safety analysis will be performed by planned dose group.

The following study phases will be defined for the analysis of adverse events (AEs):

- **Screening** (ranging from 0:00h on day of informed consent until first administration of study medication (BI/Sham))
- **On treatment** (ranging from the first time of administration of BI or Sham until 0:00h on the day after trial termination date)

Section 7.3.5 of the CTP:

Note that AEs occurring after the last per protocol contact but entered before database lock will be reported to Pharmacovigilance only and will not be captured in the trial database.

The following AE displays will be provided in the report:

In Section 15.3 and Appendix 16.1.13.1.8 (for ClinicalTrials.gov and EudraCT) of the CTR displays, the on treatment phase will be analysed (labelled with the short label of the study treatment). The screening phase will not be included in this analysis.

In Appendix 16.1.13.1.8, parts will be combined and not displayed separately.

The following totals will be provided in addition for Section 15.3.

- a total over all on treatment phases ("**Total**")

In Section 15.4 and Appendix 16.2 (Listings) of the CTR displays, the screening period will additionally be included and no totals will be provided.

For detailed information on the handling of the treatments refer to Technical TSAP ADS (analysis data set) plan and Analysis Data Reviewers guide.

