		2	3	4	5	6	
Visit	1 ⁽¹⁾	2	3	4	5	6	7
Study Day/ Week	Duration 3 to 28 days	1			85 Week 12	113 Week 16	141 Week 20
Time window for visits (days)		none	±3	±3	±7	±7	±7
Informed consent	X						
Informed consent Aqueous sampling (optional)	X						
Demographics	X						
Medical history	X						
Physical examination (including weight)	X				X		
Vital signs	X	X	X	X	X	X	X
Laboratory tests	X	X	X	X	X	X	X
12-lead ECG ⁽²⁾	X	X	X	X	X		
Review of in-/exclusion criteria	X	X					
Dose Assignment		X					
Randomization		X					
[REDACTED]		■	■	■			
Pregnancy test ⁽³⁾	Xs	Xs	Xu	Xu	Xu	Xu	Xu
[REDACTED] ⁽⁴⁾		X	X	X	X	X	X
PK [REDACTED]		■	■	■	■	■	■
[REDACTED]		X		X		X	X
BCVA testing	X	X	X	X	X	X	X
SD-OCT	X	X	X	X	X	X	X
OCT Angiography	X	X	X	X	X	X	X
Fundus Photo	X	X	X	X	X	X	X
Slit lamp and intra-ocular pressure (IOP)	X	X	X	X	X	X	X
[REDACTED]		X	X	X	X	X	X
All AEs/SAEs/AESIs	X	X	X	X	X	X	X

Trial Periods	Screening Period	Treatment Period			Follow-up Period		End of Study
Concomitant therapy	X	X	X	X	X	X	X
Completion of subject participation ⁽⁶⁾							X

- (1) Screening visit should be performed in two visits. After Informed consent is obtained, visual acuity testing, SD-OCT, OCT Angiography and fundus photography should be performed and sent to central reading service. If subject is eligible based on the results from the reading centre, the subject should return to complete the rest of the screening. In case of scheduling difficulty for certain subjects, screening can be performed in one visit.
- (2) Single ECGs are to be recorded shortly before the PK sampling at the respective time points: (Section [5.2.5](#) and [Appendix 10.1](#)).
- (3) Pregnancy testing: serum pregnancy test (Xs) is done at screening and on day 1 if more than a week elapsed between screening and day 1, and at the other visits as a reflex when urine testing (Xu) is positive.
- (4) 
- (5) See separate flow chart for Aqueous sampling (Table [10.1:3](#)). Aqueous samples are collected immediately before drug administration at Visits 2 and 4. At visits 6 and 7, when no drug is administered, the aqueous samples can be collected at any time during the visit (Section [4.1.5](#))
- (6) Completion of subject participation also needs to be completed in the eCRF if the subject withdraws prematurely following assignment to dose level (Section [3.3.4](#)).

TABLE OF CONTENTS

TITLE PAGE	1
CLINICAL TRIAL PROTOCOL SYNOPSIS	2
FLOW CHART I (PART A).....	6
FLOW CHART II (PART B).....	8
TABLE OF CONTENTS	10
ABBREVIATIONS	14

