Risks related to IVT injection	Clinical trials assessing efficacy and safety in marketed drugs administered via IVT injection showed a low rate of complications associated with IVT injection procedure. Because the procedure of intravitreal injection of BI 765128 is the same (use of a filter needle to extract product from the vial and same needle size for injection, 30 gauge), the expected adverse events related to the procedure are considered equal to what was observed with marketed drugs.	At each visit a complete ophthalmic examination will be performed to detect early signs of complications. Intra-ocular pressure (IOP) will be measured at each visit.
Risks related to blood sampling	Blood sampling may be accompanied by mild bruising and also in rare cases, by transient inflammation of the wall of the vein. In addition, in rare cases a nerve might be injured while inserting the venous catheter, potentially resulting in paraesthesia, reduced sensibility, and/or pain for an indefinite period.	The total volume of blood withdrawn during the entire study per subject will not exceed the volume of appr. 500 mL.
Risks related to Anterior Chamber tap	Corneal abrasion, cataract formation, infection, iris and lens trauma	Only experienced physicians will undertake the procedure

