7.8.1 Adverse Events

AEs will usually be coded with the most recent version of MedDRA. The version to be used will be specified in RPM. The coding version number will be displayed as a footnote in the respective outputs.

Unless otherwise specified, the analyses of AEs will be descriptive in nature. All analyses of AEs will be based on the number of subjects with AEs and NOT on the number of AEs. BI standards as presented in “Analysis and Presentation of Adverse Event Data from Clinical Trials – Display Template” [BI-KMED-BDS-HTG-0041] (9) and [BI-KMED-BDS-HTG-0066] (10) will be applied.

The analysis of AEs will be based on the concept of treatment emergent AEs. That means that all AEs will be assigned to ‘screening’ and ‘on treatment’ phases as defined in [Section 6.1](#). AEs will be analysed based on actual treatments, as defined in [Table 6.1: 1](#).

According to the clinical study protocol, adverse events of special interest (AESI) will be analysed:

Section 5.2.7.1.4 of the CTP:

The following are considered as AESIs:

- DLE
All AEs meeting the criteria for a dose limiting event (DLE) as defined in CTP Section 5.2.1 are defined as AESIs for this trial.
- Hepatic injury
A hepatic injury is defined by the following alterations of hepatic laboratory parameters:
 - *an elevation of AST (Aspartate Aminotransferase) and/or ALT (Alanine Aminotransferase) ≥ 3 -fold ULN combined with an elevation of total bilirubin ≥ 2 fold ULN measured in the same blood draw sample, or*
 - *aminotransferase (ALT, and/or AST) elevations ≥ 10 fold ULN.*

According to ICH E3 (11), in addition to Deaths and Serious Adverse Events, ‘other significant’ AEs need to be listed in the clinical trial report. These will be any non-serious adverse event that led to an action taken with study drug (e.g. discontinuation or dose reduced or interrupted).

An overall summary of AEs will be presented. The frequency of subjects with AEs will be summarised by treatment, primary system organ class (SOC) and preferred term (PT). Separate tables will be provided for subjects with

- serious AEs,
- drug-related AEs,
- drug-related serious AEs,
- ocular AEs,
- ocular AEs in the study eye,
- DLEs during study,
- DLEs during primary DLE evaluation period of 7 days (for SRD part only),
- AESIs,
- drug-related AESIs,
- other significant AEs,
- procedure related AEs.

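### An adverse event of the first aqueous tap or first eye preparation, if its onset is recorded before the first injection and it does not worsen, is left out of the summarised procedure-related AE table

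*SAP*

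**What the plan says.** SAP 6.1 defines two phases for AEs. Screening is "ranging from 0:00h on day of informed consent until first administration of study medication"; on treatment is "ranging from the first time of administration of BI or Sham until 0:00h on the day after trial termination date". The boundary is thus a clock time on Day 1, not the start of that day. For the AE displays in Section 15.3 of the trial report and the disclosure appendix, SAP 6.1 states: "The screening phase will not be included in this analysis". For Section 15.4 and the Appendix 16.2 listings, "the screening period will additionally be included and no totals will be provided".

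SAP 7.8.1 carries these phases into all AE analyses ("all AEs will be assigned to" the two phases). Among the frequency tables it lists is one for "procedure related AEs". It makes no exception for that table.

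On timing, footnote 5 of Flow Chart II in the protocol says: "Aqueous samples are collected immediately before drug administration at Visits 2 and 4". Protocol 4.1.5 describes anaesthesia, antisepsis and a lid speculum as part of the injection procedure, with the same steps before a sham injection. The risk table in protocol 1.4.2.6 names the harms of an anterior chamber tap: "Corneal abrasion, cataract formation, infection, iris and lens trauma".

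**The concern.** A cut-off at first administration suits drug-related events, because nothing before the first dose can be due to the drug. It does not suit a table of procedure-related events, where exposure begins with the procedure. At Visit 2 the tap and the preparation of the eye both fall on the wrong side of the boundary.

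Some of the named tap harms, such as corneal abrasion or iris or lens trauma, can be evident at once, so they are the ones most exposed to the cut-off. The table meant to summarise procedure harm, and the disclosure tables built on the same phase, can then understate it. A reader of the table would not see that the first procedure is only partly covered.

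**Working it through.** The plan gives no figure to reproduce. The check traces one event through the rules and then counts procedures.

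**Trace.** Take a corneal abrasion caused by the tap, recorded before any injection given that day, which does not worsen.

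| Visit (Part B) | Relation to first administration | Phase (SAP 6.1) | In the procedure-related table? |
|---|---|---|---|
| 2 | before | screening | no, listings only |
| 4 | after (before the third injection) | on treatment | yes |
| 6, 7 | after | on treatment | yes |

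This reads the SAP 7.8.1 frequency tables as Section 15.3 displays, the natural reading of SAP 6.1.

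**Worsening rule.** Protocol 7.3.5 counts an AE that begins before the first dose and worsens afterwards as treatment-emergent. SAP 6.1 and 7.8.1 do not repeat this rule. With it applied, only events that do not worsen are lost.

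**Onset time.** The boundary needs a clock time. Protocol 8.3.1 names only the onset date as mandatory. SAP 6.6 sends incomplete AE dates to a sponsor standard that is not reproduced. Its rule of setting a missing time to 23:59 concerns unscheduled ocular assessments, not AE onsets. The documents therefore do not show how a Day 1 AE without a time is assigned.

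**Share of procedures before the boundary.**
- Aqueous taps, Part B, consenting subjects: Visits 2, 4, 6 and 7, so 1/4 = 25%.
- Injection preparations, Part B: Visits 2, 3 and 4, so 1/3 = 33%.
- Injection preparations, Part A: Visit 2 only, so 1/1. Part A has no tap.

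**Illustrative size for taps.** The documents give neither a complication rate nor a consent rate. Assume 1% to 5% immediate complications per puncture, full consent, every such onset recorded before the injection and no worsening. Expected events at Visit 2 = first taps × rate.
- 20 first taps (if only the active arm is punctured): 20 × 0.01 = 0.2 to 20 × 0.05 = 1.0, out of 80 × 0.01 = 0.8 to 80 × 0.05 = 4.0 over all four taps.
- 30 first taps (if all Part B subjects are punctured): 30 × 0.01 = 0.3 to 30 × 0.05 = 1.5.

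Within the assumed rates these are ceilings, because sampling is optional and protocol 5.4 expects only a subset. For preparation of the eye, up to 18 + 30 = 48 first preparations are involved, but there is no basis for a rate.

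**The case against.** The strongest reply is that the phase is assigned by onset, not by cause, and that the interval between tap and injection is short. A reader might infer that all complications of the first tap and preparation are lost. The documents do not support that: an infection or cataract that appears later, or an abrasion first noticed after the injection, is on treatment and counted. An event that worsens is counted under protocol 7.3.5, which the SAP says it builds on. AEs are collected from consent, and those in screening still appear in Section 15.4 and the listings, so nothing is hidden. If onset times are not recorded, the sponsor standard may already place Day 1 events on treatment. All of this stands and narrows the point.

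Three further inferences are tempting and also fail.
- **Imbalance between arms.** Protocol 4.1.5 describes a sham tap but does not say who receives it, and no other section confines real taps to the active arm. An unequal omission is possible but not shown.
- **The ocular AE endpoint in Part B.** Protocol 2.1.3 defines it from drug administration, so for that endpoint the SAP follows the protocol.
- **The primary endpoints.** The Part B endpoint counts drug-related AEs from drug administration, and the Part A endpoint counts dose limiting events from the same point. A pre-dose procedural event has essentially no bearing on either.

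What the reply does not remove is the rule itself. For an onset recorded before the injection, the exclusion is written in the SAP, and nothing in either document brings a non-worsening event back into the procedure-related table.

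**Conclusion.** The point holds in a narrow form. An AE of the first tap (consenting Part B subjects) or first eye preparation (both parts), with recorded onset before the first administration and no later worsening, is omitted from the summarised procedure-related table, while the same event at a later visit is counted. The table can therefore understate procedure risk.

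The expected size is low. The number of events cannot be derived from the documents; for taps it is probably no more than about one, given the assumed rates, and the contribution of eye preparation cannot be sized. The conclusion assumes that onset is recorded with a time. It is a cheap improvement to one safety table and does not threaten the trial's main conclusions.

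**What to change.** In SAP 6.1 and 7.8.1:
- Let the procedure-related table also include AEs flagged as procedure-related with onset on Day 1 at or after the first trial procedure of Visit 2. Add a footnote stating that this table starts earlier than the other AE tables.
- State that procedure-related AEs with onset on Day 1 and no onset time are included in this table.
- Carry the worsening rule of protocol 7.3.5 into the SAP.
- Leave the drug-related AE endpoint and the protocol-defined ocular AE endpoint unchanged.

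The cost is a few sentences and a small change to the derivation of one table. No new data are needed, since protocol 5.2.7.2.1 already collects all AEs from informed consent. The downside is that this table's observation period would differ slightly from that of the overall AE summary, so its events would no longer be strictly a subset of the AEs summarised there. The footnote covers this.
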